6.1.7.3 Treatment Regimen

Each subject will receive a single treatment with QM1114-DP and/or placebo at the baseline visit.

The treatments investigated in this study are:

- 60 U of QM1114-DP in the LCL
- 50 U of QM1114-DP in the GL
- Placebo

6.2 Study Product Packaging and Labeling

QM1114-DP and placebo are manufactured under aseptic conditions. **CCI**

The labels will be printed in English. The text of the label will detail the information requested by Good Manufacturing Practice and local regulations, and at a minimum include the protocol number, storage conditions, and an investigational test article disclaimer ("Caution: New Drug - Limited by Federal (or United States) law to investigational use.")

6.3 Supplies Management

6.3.1 Accountability

Upon receipt of the study products, the Investigator or designee will maintain accurate records of the study products delivery to the clinical study center, the inventory at the clinical study center, the use by each subject, the reconciliation of all study products received from the Sponsor's designee, and the return to the Sponsor's designee for disposal of unused study products.

All study products sent to the Investigator/Institution will be accounted for and no unauthorized use is permitted.

6.3.2 Storage of Study Products

Study products must be stored in a safe and secure area with restricted access, under the storage conditions specified by the Sponsor (see [Table 3](#)).

6.3.3 Dispensing and Return

All study products must be inventoried and a record of the dispensing for each subject must be appropriately documented. Any dispensing errors must be reported to the Sponsor/CRO and properly documented.

 GALDERMA	Title 43QMI902 Clinical Study Protocol - QM1114 - LCL and GL	Doc id MA-40371
--	---	----------------------------------

Effective date: 2020-06-09 07:02

Effective

Version: 4.0

In the event of early termination/suspension of the clinical study, a rapid recall of study products will be initiated.

Unused or expired study product will be returned for destruction to the Sponsor representative at time points approved by the Sponsor.

6.3.4 Treatment Compliance Management and Record

The treatment is an injection administered by the Investigator. Details of the injection procedure will be recorded in the eCRF and subject source documents. No other measurements of treatment compliance will be made.

6.3.5 Dose Modification

Dose modifications are not permitted.

6.3.6 Product Quality Complaints

Product Quality complaints (PQCs) should be reported to the Safety e-mail listed in Section [11.9](#). A PQC is an external judgement presuming a quality defect of a product; quality issue for a product relating to its presentation or use, identified by a subject, a practitioner or Investigator site personnel, a distributor, or anyone else involved in clinical supplies handling. Examples may include but are not limited to appearance issues, odor, damaged stoppers, low fills, and foreign matter in the product. These complaints may or may not represent a potential risk to the subject. A PQC form must be completed by the study center personnel and forwarded to the Sponsor or designee within 24 hours of awareness. Affected study product should be quarantined, and not used, until further notice by the Sponsor.

Additional contact details are provided in the Investigator's site file.

6.4 Blinding

This is a double-blind study in which neither the Investigator, sub-Investigator, study staff, nor the subject will know the subject's study product assignment (i.e., QM1114-DP and/or placebo). Placebo is identical in appearance to QM1114-DP but contains no active drug substance.

Subjects will be randomized at baseline to either treatment with QM1114-DP, QM1114-DP and placebo, or placebo. In order to maintain the blind, the study products, will be supplied in identical vials, each with a unique number on the vial label. Both study products will be administered in exactly the same way.

An un-blinded statistician will generate the randomization schedule; however, he/she will not be involved in any other aspect of the study prior to database lock.

 GALDERMA	Title 43QMI902 Clinical Study Protocol - QM1114 - LCL and GL	Doc id MA-40371
--	---	----------------------------------

Effective date: 2020-06-09 07:02

Effective date:

Effective

Version: 4.0

The Sponsor's staff or designees directly involved in clinical operations management, data management, and statistical evaluation of the study will remain blinded until the database is locked, unless emergency unblinding is required.

6.4.1 Verification of Blinding

The Sponsor's staff or designees will assess and verify maintenance of the study blind during the study through routine monitoring visits.

6.4.2 Unblinding During the Clinical Study

Emergency un-blinding during the clinical study may be required for therapeutic or for regulatory reasons (for expedited safety reporting).

A blind-break system will be available for Investigators. In such an emergency, the Investigator will only break the blind for the subject involved.

The Investigator must notify the Sponsor immediately in the event of such an emergency (see contact details in Section 7.2.6.2.2). If possible, the Investigator should notify the Sponsor before breaking the blind in order to discuss this decision with the Sponsor. The Investigator is required to document each case of emergency unblinding and inform the Sponsor immediately.

7. CLINICAL STUDY ASSESSMENT

7.1 Efficacy Assessments

7.1.1 Investigator 4-point Photographic Scale of Lateral Canthal Line Severity (LCL-ILA)

The validated Investigator 4-point Photographic Scale of Lateral Canthal Line Severity (LCL-ILA) (Appendix 1), developed by Galderma, includes two grading systems: one for the Investigator live assessments at maximum smile, **CCI** [REDACTED].

The scale represents LCL severities from none (grade 0), mild (grade 1), moderate (grade 2), to severe (grade 3). Each grade is also depicted by an individual photograph and descriptive text. The Investigators will be trained on the use of the LCL-ILA.

The Investigators will use the LCL-ILA for direct, live comparison with the subject's face for grading LCL severity at screening, baseline (prior to treatment), and at all post-treatment visits. Left and right LCL should be assessed separately at **CCI** [REDACTED] maximum smile.

 GALDERMA	Title 43QMI902 Clinical Study Protocol - QM1114 - LCL and GL	Doc id MA-40371
--	---	----------------------------------

7.1.2 Subject 4-point Photographic Scale of Lateral Canthal Line Severity (LCL-SLA)

The validated Subject 4-point Photographic Scale of Lateral Canthal Line Severity (LCL-SLA) ([Appendix 2](#)), developed by Galderma, includes two grading systems: one for the subject's live assessments at maximum smile, **CCI**. The scale represents LCL severities from Level 0, Level 1, Level 2, to Level 3. Each grade is also depicted by an individual photograph and descriptive text. Subjects will be trained on the use of the LCL-SLA.

Subjects make their assessments independently of the Investigator's assessment. Subjects will evaluate their LCL severity (left and right side separately) at **CCI** maximum smile, respectively, at screening, baseline (prior to treatment), and at all post-treatment visits.

7.1.3 Investigator 4-point Photographic Scale of Glabellar Line Severity (GL-ILA)

The validated Investigator 4-point Photographic Scale of Glabellar Line Severity (GL-ILA) ([Appendix 3](#)) includes two grading systems: one for Investigator live assessments at maximum frown, **CCI**. The scale represents the severity of GL from none (grade 0), mild (grade 1), moderate (grade 2) to severe (grade 3). Each grade is also depicted by an individual photograph and a descriptive text. The Investigators will be trained on the use of the 4-point Photographic Scale.

The Investigators will use the 4-point Photographic Scales for direct, live comparison with the subject's face at **CCI** at maximum frown at screening, baseline (prior to treatment), and at all post-treatment visits.

7.1.4 Subject Static 4-point Categorical Scale of Glabellar Line Severity (GL-SLA)

Subjects will make their assessment of glabellar line severity independently of the Investigator's assessment. Subjects will be asked to evaluate their GL at maximum frown at screening, baseline (prior to treatment), and at all post-treatment visits using the following Static 4-Point Categorical Scale.

Grade	Severity of Glabellar Lines	Description
0	No wrinkles	Smooth skin
1	Mild wrinkles	Fairly smooth skin
2	Moderate wrinkles	Frown lines
3	Severe wrinkles	Deep frown lines

CCI

[figure not shown]

Effective date: 2020-06-09 07:02

Effective

Version: 4.0

CCI

 GALDERMA	<small>Title</small> 43QMI902 Clinical Study Protocol - QM1114 - LCL and GL	<small>Doc id</small> MA-40371
--	---	--

CCI

7.2 Safety Assessments

Safety assessment will be conducted for all subjects at the time points indicated in Schedule of Assessments ([Table 2](#)). Safety parameters include an evaluation of AEs, **CCI** vital signs, ECG, laboratory safety tests (chemistry and hematology), and neutralizing antibody production.

7.2.1 Focused Physical Examination (FPE)

At the time points indicated in the Schedule of Assessments ([Table 2](#)), the Investigator or designee will perform a physical examination of the subject that includes the face, head, and neck. Further details are provided in [Appendix 6](#).

Post-baseline, the signs and symptoms will also be monitored via physical examination of face, head, and neck to evaluate local effect of toxin. In addition, general physical examination to evaluate the remote spread events will be conducted. The list of remote spread of toxin events is considered while doing clinical evaluations based on subject's symptoms and signs ([Appendix 7](#)). Directed questioning and examination will then be performed as appropriate.

The Investigator may choose to investigate any other sign that he/she observes during the physical examination. Abnormalities noted pre-injection, i.e. at the screening/baseline visits, should be recorded as medical history and abnormalities noted post-injection should be recorded as AEs.

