5.2.2 Exclusion Criteria

1. Botulinum toxin treatment in facial areas within 9 months prior to study treatment.
2. Anticipated need for treatment with botulinum toxin of any serotype for any reason during the study (other than the investigational product).
3. Female who is pregnant, breast feeding, or intends to conceive a child during the study
4. Known allergy or hypersensitivity to any component of the investigational product (QM1114-DP).
5. Inability to substantially reduce the appearance of facial rhytides in the treatment area by physically spreading them apart, as determined by the Investigator.
6. Clinically significant abnormal focused physical examination finding(s) at screening or baseline visits, in the investigator's opinion.
7. Excessive skin laxity in the treatment area or periorbital area.
8. Previous use of any hyaluronic acid soft tissue augmentation therapy in the lateral canthal or glabella area within 6 months before baseline.

 GALDERMA	Title 43QMI902 Clinical Study Protocol - QM1114 - LCL and GL	Doc id MA-40371
--	---	----------------------------------

Effective date: 2020-06-09 07:02

Effective

Version: 4.0

9. Previous soft tissue augmentation with any permanent (non-biodegradable such as silicone, polyacrylamide, etc.) or semi-permanent (e.g., calcium hydroxylapatite, Poly-L-Lactic acid or polymethyl-methacrylate) product; lifting threads, or autologous fat in the treatment area.
10. History, presence, or predisposition of eyelid or eyebrow ptosis (heavy eyebrows), amblyopia (i.e., lazy eye), or previous surgery around the eye that may lead to the above events, as determined by the Investigator.
11. Marked facial asymmetry, excessive dermatochalasis (i.e., excess of skin in eyelids), or marked periocular or eyebrow asymmetry.
12. Presence of scar(s), piercing(s), or tattoos (including microblading of eyebrow or eyeliner) in the treatment area or around the treatment area, that in the Investigator's opinion, may interfere with study evaluations.
13. Presence of inflammation, active infection or skin disorder, such as eczema, rosacea, facial psoriasis, herpes zoster etc., near or in the treatment area.
14. Presence of cancerous or pre-cancerous lesions in the treatment area.

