7.2.2 Vital Signs

At the time points indicated in the Schedule of Assessments ([Table 2](#)), evaluation of vital signs shall be performed after approximately 10 minutes rest in the sitting position. It shall include measurement of systolic and diastolic blood pressure, heart rate, and respiratory rate. Vital signs will be taken prior to any blood draw, excluding post-treatment measurements on Day 0.

 GALDERMA	Title 43QMI902 Clinical Study Protocol - QM1114 - LCL and GL	Doc id MA-40371
--	---	----------------------------------

All abnormal values at the baseline visit identified, as clinically significant by the Investigator, shall be recorded in the Medical History form.

For any clinically significant changes from the baseline visit, an AE is to be recorded.

7.2.3 **Electrocardiogram (ECG)**

The 12-lead ECG recordings will be made after the subjects have been resting in a supine position for at least 10 minutes at the time points indicated in [Table 2](#), the baseline ECG should be done prior to treatment. The subjects should avoid postural changes during the ECG recordings. At each time-point, the ECG will be recorded in triplicate. The triplicates will be performed at approximately one-minute intervals.

ECGs will be stored electronically and submitted to a central reviewer for analysis. Paper printouts may also be collected for general cardiac safety monitoring at the clinical research site.

Clinically significant abnormal values at baseline shall be recorded in the Medical History form. For any clinically significant changes from baseline, an AE is to be recorded.

The Investigator and Medical Monitor will be alerted (eg, email) for ECGs that are identified as “abnormal, clinically significant” by the central ECG laboratory.

7.2.4 **Laboratory Safety Tests**

Blood samples will be collected at baseline (prior to treatment) and at Month 6/ET, and sent to a central laboratory for analysis. Instructions for blood sampling are detailed in a separate laboratory manual.

The following laboratory safety tests shall be performed:

- Hematology: White blood cell (WBC) count with differential, red blood cell (RBC) count, haemoglobin (Hb), hematocrit (hct), and platelet count (Plt)
- Blood chemistry: Creatinine, urea nitrogen, gamma glutamyl transferase (GGT), alkaline phosphatase (ALP), aspartate aminotransferase (AST=SGOT), alanine aminotransferase (ALT=SGPT), and bilirubin (total and conjugated)

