7.2.6.1 Definitions

7.2.6.1.1 Adverse Events (AE)

According to ICH E2A,¹⁵ an AE is any untoward medical occurrence in a patient or a clinical investigation subject administered a pharmaceutical product and which does not necessarily have a causal relationship with this treatment. An AE can therefore be any unfavorable and unintended sign (including an abnormal laboratory finding), symptom, or disease temporally associated with the use

 GALDERMA	Title 43QMI902 Clinical Study Protocol - QM1114 - LCL and GL	Doc id MA-40371
--	---	----------------------------------

Effective date: 2020-06-09 07:02

Effective

Version: 4.0

of a medicinal (investigational) product, whether or not related to the medicinal (investigational) product.

Thus, any new sign, symptom or disease, or any clinically significant worsening of an existing sign, symptom or disease (including new episodes of a chronic disease [e.g., hay fever, allergy]) compared to the condition at the first visit, should be considered as an AE. Lack of efficacy is not considered as an AE.

Notes:

- There should be an attempt to report a diagnosis rather than the signs, symptoms or abnormal laboratory values associated with the report of an AE. However, a diagnosis should be reported only if, in the Investigator's judgment, it is relatively certain. Otherwise, symptoms, signs, or laboratory values should be used to describe the AE.
- Pregnancy is not to be considered as an AE; however, is an important medical event that must be monitored as described in Section [7.2.6.2.3](#).
- The effects of all BoNT products may spread from the area of injection to produce symptoms consistent with BoNT effects. These symptoms have been reported hours to weeks after injection. Remote spread of toxin that affects swallowing and breathing can be life threatening, and there have been reports of death. The risk of symptoms is increased in subjects who have underlying conditions (e.g. disorders of the neuromuscular junction) that would predispose them to these symptoms. BoNT is contraindicated in individuals with known hypersensitivity to any BoNT preparation or to any of the components in the formulation.

7.2.6.1.2 *Treatment Emergent Adverse Event (TEAE)*

A TEAE is an event that emerges during treatment, having been absent pre-treatment, or worsens relative to the pretreatment state.

7.2.6.1.3 *Serious Adverse Events (SAE)*

A SAE is any untoward medical occurrence that at any dose:

- Results in death,

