Appendix 6 Focused Physical Examination Form Example

Not done Provide details: _____

General Health Assessment

Complete at Screening, Baseline (prior to treatment), Day 7, Day 14, Months 1 and 6/ET

Question the subject about their general health (general wellbeing/ bodily functions, e.g., arms, legs, stomach/ bladder/ bowel, also refer to the list of Adverse Events Potentially Suggestive of Distant Spread of Toxin ([Appendix 7](#))). Abnormalities noted pre-injection should be recorded as medical history and Investigator should confirm if any abnormalities affect subject eligibility. Abnormalities noted post-injection should be documented as AEs.

Next, proceed to the Focused Physical Examination (Part 1 and 2) as indicated below.

Part 1:

Complete at Screening, Baseline (prior to treatment), Day 7, Day 14, Months 1 and 6/ET

Please perform a targeted examination of the face, head, and neck recording abnormalities.

Part 1 Examination	Normal	Abnormal* (provide details)
Eyelid position		
Eyebrow position		
Vision abnormalities (not refractive errors)		
Throat function (e.g., swallowing/drink water)		
Ability to talk and chew		
Ability to stick out and move tongue		
Ability to lift shoulders		

* Abnormal findings at the screening and baseline visit, noted pre-injection, should be recorded as medical history and the Investigator should confirm if any abnormalities affect subject eligibility. Abnormalities noted after study treatment should be documented as AEs.

Investigator Signature

Date

 GALDERMA	Title 43QMI902 Clinical Study Protocol - QM1114 - LCL and GL	Doc id MA-40371
---	--	----------------------------------

PART 2: Complete at Day 7, Day 14, Months 1 and 6/ET

Not done **Provide details:** _____

After questioning the subject about their general health and performing Part 1, determine if there are any **clinically significant abnormalities** that may suggest local or remote spread of toxin effect.

- Local Spread of Toxin Effect refers to effects in areas adjacent to the treatment area (e.g., lower frontalis or medial part of temporalis).
- Remote Spread of Toxin Effect refers to effects in other body parts, not adjacent to the treatment area, when effect can only be attributed to the toxin and there is no other medically sound cause.
- Determine if the event is clinically significant (i.e., would affect subject safety, confound the study data, or requires medical treatment) and document on the source document.

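### The FPE rule for recording AEs omits the new-or-worsened test in the protocol's AE definition, and the SAP's onset-only TEAE rule would not reliably screen out an unchanged finding recorded because of it

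*Protocol*

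**What the plan says.** Protocol 7.2.1 sorts focused physical examination (FPE) findings by when they are noted. "Abnormalities noted pre-injection, i.e. at the screening/baseline visits, should be recorded as medical history", and the same sentence continues that "abnormalities noted post-injection should be recorded as AEs".

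The example form in Appendix 6 carries the rule in two places. The General Health Assessment says "Abnormalities noted post-injection should be documented as AEs". The footnote to the Part 1 column for abnormal results says "Abnormalities noted after study treatment should be documented as AEs". Part 2 has a similar footnote, but its scope is restricted to "clinically significant abnormalities" that may suggest local or remote spread of toxin.

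The AE definition in 7.2.6.1.1 covers a new sign, symptom or disease, or "any clinically significant worsening of an existing sign, symptom or disease", compared with the first visit. For vital signs, 7.2.2 states: "For any clinically significant changes from the baseline visit, an AE is to be recorded". Section 7.2.3 has the equivalent rule for ECGs. Section 7.2.4 asks that a clinically significant laboratory abnormality was absent at baseline or has worsened.

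The protocol defines a TEAE (7.2.6.1.2) as an event absent before treatment or worse than the pre-treatment state. SAP 1.5.1 defines it by onset at or after the time of treatment and nothing else.

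**The concern.** FPE is the only one of these four safety assessments whose AE rule has no comparison with baseline. Subjects can enter the trial with an abnormal FPE finding, because exclusion criterion 6 removes only a "Clinically significant abnormal focused physical examination finding(s) at screening or baseline visits", as judged by the investigator. A lesser finding goes into medical history. If it is still present at Day 7, a site following the form literally opens an AE, and a site following 7.2.6.1.1 does not.

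TEAE incidence and severity is a listed safety endpoint. At stake are its accuracy and its consistency across sites. An unchanged pre-existing finding should not appear there, and whether it does should not depend on which protocol section a site happened to follow.

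**Working it through.** No figure in the plan is in dispute and no arithmetic decides the point. The check is a comparison of texts followed by one path through the SAP's rules.

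**1. Baseline comparison in each recording rule**

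| Source | Comparison required before a post-treatment finding becomes an AE |
|---|---|
| AE definition, 7.2.6.1.1 | New, or clinically significant worsening |
| Vital signs, 7.2.2 | Clinically significant change from baseline |
| ECG, 7.2.3 | Clinically significant change from baseline |
| Laboratory, 7.2.4 | Clinically significant, and absent at baseline or worsened |
| FPE, 7.2.1 | None stated |
| Appendix 6, General Health | None stated |
| Appendix 6, Part 1 footnote | None stated |
| Appendix 6, Part 2 | None stated, but limited to clinically significant findings suggesting spread |

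**2. Opportunity.** General Health and Part 1 are completed at screening, baseline, Day 7, Day 14, Month 1 and Month 6/ET, so there are four scheduled post-treatment examinations. The Part 1 example form offers only normal or abnormal, with no option for unchanged.

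**3. From AE to TEAE.** Suppose a subject has a minor finding in medical history, unchanged at Day 7, and the site records an AE.

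- Under protocol 7.2.6.1.2 it is not a TEAE, because it was present before treatment and has not worsened.
- Under SAP 1.5.1 with a complete and correct pre-treatment onset date, it is not a TEAE.
- Under SAP 1.5.1 with a post-treatment onset date entered, for example the visit date, it is a TEAE.
- Under SAP 2.5.2 with the start date completely missing, onset becomes the treatment date, so it is a TEAE.
- Under SAP 2.5.2 with only the day missing, the first of the month is used. If that falls before treatment, the date is replaced by the treatment day, so it is a TEAE even when the recorded month and year lie before treatment.
- Under SAP 2.5.2 with the month or the year missing, an imputed date before treatment is moved to the following month or year after treatment, so it is a TEAE.

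Long-standing findings plausibly have incomplete onset dates, so these imputation routes matter. SAP 2.8, which lists departures from the protocol's analyses, does not mention the narrower TEAE test.

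**4. Size.** The documents give no rate of abnormal baseline FPE findings, so the number of affected subjects cannot be derived. As a scale only, assume that 2% to 10% of the 413 subjects carry such a finding: 0.02 × 413 ≈ 8 and 0.10 × 413 ≈ 41. Those are counts of carriers. They would equal false TEAEs only if every carrier were recorded as an AE with a post-treatment or imputed onset.

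**The case against.** The strongest reply is that 7.2.1 is a two-way rule. A finding noted before injection has already been assigned to medical history, so noted post-injection can mean first noted then, which agrees with the AE definition. No sentence expressly says that an unchanged finding must be recorded again. This reading is available, so the fault is an unqualified rule and not an explicit instruction. It is not the only natural reading, however. Section 7.2.1 explains the pre-injection half by visit, and the Part 1 footnote hangs on a column that is ticked afresh at each examination.

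Four further points narrow the matter, and they stand:

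- **Eligibility.** Besides criterion 6, exclusions 7, 10, 11 and 17 remove excessive periorbital laxity, ptosis or predisposition to it, marked eyebrow or periocular asymmetry, facial palsy and neuromuscular conditions. Part 1 also leaves out refractive errors. Much of the eyelid and eyebrow pool is gone, though stable general-health complaints remain.
- **Spread tables.** A reader might infer that false events would swamp the detection of toxin spread. The documents do not support that. Part 2 is limited as described, the investigator judges each suspected event (SAP 2.5.2.2), and spread has its own tables.
- **Dilution.** A reader might also infer a distorted comparison of arms. If true TEAE rates were 10% and 5%, and 5 points were added to each, the ratio would fall from 10/5 = 2.0 to 15/10 = 1.5. All of these inputs are assumed, the difference stays at 5 points, and the SAP plans descriptive safety summaries with no such ratio.
- **Visibility.** The FPE shift table (SAP 2.5.5) and the medical-history and FPE listings would show an unchanged abnormality. They do not correct the TEAE tables.

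Appendix 6 is also only an example form, and the eCRF in use is not shown.

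**Conclusion.** The inconsistency is real and should be corrected. The FPE recording rule is wider than the protocol's own AE definition, and the SAP's TEAE rule is looser than the protocol's, so an unchanged pre-existing finding recorded under the first can survive the second.

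The texts do not support saying that the form necessarily creates false TEAEs. That takes three things together: a non-exclusionary baseline abnormality, a site that reads the rule literally, and either a post-treatment onset date or a missing or partial one. The size is unknown and probably small. Efficacy, sample size and the inferential analyses are untouched.

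**What to change.** 1. In Protocol 7.2.1 and the Appendix 6 instructions, state that a post-injection FPE abnormality is documented as an AE when it is new, or is a clinically significant worsening, relative to the pre-injection examination. Keep the words clinically significant, so that the rule matches 7.2.6.1.1.
2. In SAP 1.5.1, align the TEAE definition with Protocol 7.2.6.1.2: absent before treatment, or worsened. Date imputation alone would then no longer turn an unchanged finding into a TEAE.
3. Before database lock, check AEs that arose from the FPE against medical history and the pre-injection examination. Protocol version 4.0 was issued while the study was running, so rewording alone would not reach forms already completed.

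The cost is a change of wording in one section and one form, a note to sites, a revised SAP definition and a small data check. The downside is that sites must consult the pre-injection form when they record a finding. All abnormal FPE results still appear in the listings and the shift table, so no examination data are lost.
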